3.8.6 Other Safety Evaluations

3.8.6.1 Vital Signs

Vital sign results, as well as changes from baseline, will be summarized with descriptive statistics by visit. Treatment-emergent laboratory/vital signs changes (TELVC) will be defined for post-baseline values according to the reference ranges given in **Appendix F**. Number of subjects with TELVC will be summarized by visit.

For dosing visits, only measurements prior to dosing will be considered for by-visit presentations. In the case of multiple measurements prior to dosing, the first measurement will be used for by-visit presentations, but all measurements will be considered for the TELVC classification.

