 - Urine β-HCG (dipstick; females of childbearing potential only, ensure result is negative)
- 4. Assess worsening and/or flare of SLE disease activity using SLE Increase in Disease Activity CRF and complete for SLE related AEs that are not serious, if applicable
- 5. Evaluate subject for signs and symptoms of TB using a TB surveillance form
- 6. Take vital signs before administration of investigational product (within 15 minutes of the beginning of the investigational product infusion)
- 7. Administer investigational product
 - Take vital signs (BP, pulse, respiration, and temperature) approximately every 15 (± 5) minutes during the infusion, immediately after completion of the infusion, approximately 30 (± 5) and 60 (± 5) minutes after completion of administration of

investigational product, and every 30 (\pm 5) minutes thereafter or until stable and ready for discharge (as judged by the investigator)

8. Assess for AEs/SAEs/AESIs (nonserious AEs will only be captured during the first year of the subject's participation in the study; however, nonserious AEs that result in interruption of investigational product and/or discontinuation from the study will be captured at any time during the subject's participation in the study)

5.1.2.3 Every 12 Weeks; Weeks 12, 24, 36, 48, 60, 72, 84, 96, 108, 120, 132, and 144 (Visits 4, 7, 10, 13, 16, 19, 22, 25, 28, 31, 34, and 37)

In addition to procedures and assessments performed Q4W, the following are to be performed **every 12 weeks (Q12W)**:

- 1. Collect **predose** blood samples for:
 - Serum chemistry
 - Hematology
 - QuantiFERON-TB Gold (QFT-GIT; TB testing, only if indeterminate at any visit during Study CD-IA-MEDI-546-1013)
 - SLEDAI-2K-associated lab tests (C3, C4, CH50, anti-dsDNA)
 - Pharmacokinetics (MEDI-546 serum concentration; Weeks 12, 24, 36 and 48 only)
 - Pharmacodynamics (type I IFN signature with 21-gene assay; Weeks 12, 24, 36 and 48 only)
 - Immunogenicity (ADA to MEDI-546; Weeks 12, 24, 36 and 48 only)
 - Proteomics/biomarkers (Weeks 12, 24 and 48 only; optional)
- 2. Collect urine sample for:
 - Urinalysis
 - SLEDAI-2K-associated lab tests: urine protein/creatinine ratio
 - Urine biomarker (optional)
- 3. Perform SLEDAI-2K

5.1.2.4 Every 24 Weeks; Weeks 24, 48, 72, 96, 120 and 144 (Visits 7, 13, 19, 25, 31, and 37)

- 1. Administer SF-36v2 (should be completed prior to any clinical assessments)

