7 STATISTICAL CONSIDERATIONS

7.1 General Considerations

Data will be provided in data listings sorted by SID number. Categorical data will be summarized by the number and percentage of subjects in each category. Continuous variables will be summarized by descriptive statistics, including mean, standard deviation, median, minimum, and maximum. Baseline will be defined as the Day 1 value of this OLE study prior to investigational product administration. Details of endpoint analyses will be described in the Statistical Analysis Plan.

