- 21. Table 5.1-2 (Schedule of Study Procedures for the 85-day Follow-up Period) renumbered follow-up visits (to Visits 41-43), which follow the extended treatment period; added that subjects should be evaluated for signs and symptoms of TB using a TB surveillance form at V41, V42, and V43; clarified that the SLICC assessment included ACR; and clarified that the investigator flare question is to assess worsening and/or flare of SLE disease activity.
- 22. Section 5.1.2.1 (Week 0; Day 1: First Infusion [Visit 1]), Section 5.1.2.2 (Every 4 Weeks; Weeks 4 to 152: Second through Thirty-ninth Infusion [Visits 2 to 39]), and Section 5.1.2.6 (Week 156; Last Treatment Visit [Visit 40]) - removed vital signs assessment (formerly Number [No.] 7) as vital signs will be taken before administration of investigational product (within 15 minutes of the beginning of the investigational product infusion; now No. 16); clarified that ECGs are required at Day 1 if not done at Day 396 of Study CD-IA-MEDI-546-1013; moved assessment for Cushingoid features from No. 21 to No. 8 (and added that if this assessment was performed on Day 365 of Study CD-IA-MEDI-546-1013, then data can also be used for Day 1 of this study); clarified that for all remaining assessments, if Day 1 of this study occurs on the same day as Day 422 (+ 28 days) of Study CD IA MEDI-546-1013, then the procedures and samples can be collected one time and can be utilized for both studies, and that if Day 1 of this study does not occur on the same day as Day 422 (+ 28 days) of Study CD-IA-MEDI-546-1013, then the procedures and samples should be collected at Day 1; moved assessment for physical examination from No. 17 to No. 9; and combined collection of all predose blood samples (formerly No. 9 and No. 19) under No. 10.
- 23. Section 5.1.2.1 (Week 0; Day 1: First Infusion [Visit 1]), Section 5.1.2.2 (Every 4 Weeks; Weeks 4 to 152: Second through Thirty-ninth Infusion [Visits 2 to 39]), Section 5.1.2.6 (Week 156; Last Treatment Visit [Visit 40]), Section 5.1.3.1 (28 Days after the Last Dose [± 7 Days]): First Safety Follow-up Visit or early Discontinuation Visit [Visit 41]), Section 5.1.3.2 (59 Days after the Last Dose [± 7 Days]: Second Safety Follow-up Visit

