[Visit 42]), Section 5.1.3.3 (85 Days after the Last Dose [\pm 7 Days]: Third Safety Follow-up Visit [Visit 43]), and Section 5.1.4 (Unscheduled Visit) - clarified that in addition to assessing worsening and/or flare of SLE disease activity using the SLE Increase in Disease Activity CRF, complete the CRF for SLE related AEs that are not serious, if applicable.

- 24. Section 5.1.2.1 (Week 0; Day 1: First Infusion [Visit 1]), Section 5.1.2.2 (Every 4 Weeks; Weeks 4 to 152: Second through Thirty-ninth Infusion [Visits 2 to 39]), Section 5.1.2.6 (Week 156; Last Treatment Visit [Visit 40]), Section 5.1.3.1 (28 Days after the Last Dose [± 7 Days]): First Safety Follow-up Visit or early Discontinuation Visit [Visit 41]), Section 5.1.3.2 (59 Days after the Last Dose [± 7 Days]: Second Safety Follow-up Visit [Visit 42]), Section 5.1.3.3 (85 Days after the Last Dose [± 7 Days]: Third Safety Follow-up Visit [Visit 43]), and Section 5.1.4 (Unscheduled Visit) added procedure that subjects should be evaluated for signs and symptoms of TB using a TB surveillance form.
- 25. Section 5.1.2.2 (Every 4 Weeks; Weeks 4 to 152: Second through Thirty-ninth Infusion [Visits 2 to 39]), Section 5.1.2.6 (Week 156; Last Treatment Visit [Visit 40]), and Section 5.2.5 (Clinical Laboratory Tests) clarified for hepatitis B virus DNA PCR TaqMan assessment, subjects with isolated hepatitis B core antibody positivity during Study CD IA MEDI 546-1013 or at any time for the duration of this study will be tested monthly for HBV DNA. To remain eligible for this study, the subject's HBV DNA levels must remain undetectable as per the central lab (ie, < 29 IU/mL HBV DNA detected).

- 26. Section 5.1.2.2 (Every 4 Weeks; Weeks 4 to 152: Second through Thirty-ninth Infusion [Visits 2 to 39]) renumbered individual weeks (Weeks 4 to 152), infusions (second through thirty-ninth), and visits (Visits 2-39) for clarity and consistency; changed "Week 100" to "Week 152" due to the extension of the treatment period by an additional year; removed "if indicated" from "Take vital signs (BP, pulse, respiration, and temperature, if indicated)", as temperature should always be taken after administration of investigational product, and added that vital signs should be taken "...until the subject is stable and ready for discharge (as judged by the investigator)"; and removed vital signs assessment (No. 2) since vitals are taken during administration of investigational product (No. 7).

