3 STATISTICAL METHODS

3.1 General Considerations

Categorical data will be summarized by the number and percentage of subjects in each category. Continuous variables will be summarized by descriptive statistics, including mean, standard deviation, median, minimum, and maximum. Data will be provided in data listings sorted by treatment group and subject identification (SID) number.

Baseline will be defined as the last non-missing observation on or before Day 1 prior to investigational product administration of study CD1145.

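### When a dosing visit has several pre-dose vital-sign readings, the SAP compares the first of them with a baseline that is the last pre-dose reading

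*SAP*

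**What the plan says.** **Baseline.** SAP 3.1: "Baseline will be defined as the last non-missing observation on or before Day 1 prior to investigational product administration of study CD1145". Protocol 7.1 is less specific: "Baseline will be defined as the Day 1 value of this OLE study prior to investigational product administration". It does not say which value counts if Day 1 has several.

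**Visit value.** SAP 3.8.6.1 restricts by-visit vital signs at dosing visits to pre-dose readings and adds: "In the case of multiple measurements prior to dosing, the first measurement will be used for by-visit presentations". The sentence continues: "but all measurements will be considered for the TELVC classification".

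**What is reported.** SAP 3.8.6.1: "Vital sign results, as well as changes from baseline, will be summarized with descriptive statistics by visit". Under SAP 3.2.2 these tables are for Anifrolumab Total only.

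**How many readings there are.** The current visit lists have one pre-dose set; for Day 1, Protocol 5.1.2.1 reads "Take vital signs before administration of investigational product (within 15 minutes of the beginning of the investigational product infusion"). The Amendment 4 log in Protocol 15 shows that the dosing-visit lists used to contain another vital-signs step. Item 22, covering Day 1, the four-weekly visits and the last treatment visit: "removed vital signs assessment (formerly Number [No.] 7) as vital signs will be taken before administration of investigational product". Item 26, covering the four-weekly visits: "removed vital signs assessment (No. 2) since vitals are taken during administration of investigational product (No. 7"). The log is used here only as evidence of how data may have been collected. It is not set against the current text as a contradiction.

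**The concern.** A change from baseline is interpretable when the same kind of reading is taken at both ends. Here one end is the last pre-dose reading and the other, where there is a choice, is the first. If first and last readings differ on average, for example because a subject has rested between them, the mean change includes that difference even when nothing has changed between visits.

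Vital signs are among the supporting safety variables for the primary objective (Protocol 7.3.1). The study has one open-label arm, so comparison with baseline is the main way to read these tables. Amendment 4 removed the additional vital-signs step and also changed the dose. Any offset may therefore shrink over the same period as the dose change, and the pooled tables would not separate the two.

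**Working it through.** The plan states no figure on this point, so there is none to reproduce. The check compares the two selection rules.

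**Step 1: which rule governs baseline.** SAP 3.8.6.1 gives no vital-sign baseline, and its first-reading rule is limited to by-visit presentations. SAP 3.1 therefore applies. The visit windows in SAP 3.1.1 choose by assessment day and do not choose between two readings on one day.

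**Step 2: the reported change when the true change is zero.** Let d be the mean of (first − last) pre-dose reading within a visit. Assume that a single pre-dose reading behaves like the last one, as the current near-infusion set would.

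| Readings at the visit | Value used | Baseline used | Expected change |
|---|---|---|---|
| Several | first | last | d |
| One | that reading | last | 0 |
| Day 1, several | first | last | d (should be 0) |

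**Step 3: offset in a visit mean.** If a share p of the records at a visit has several pre-dose readings, the expected offset is p × d. The documents give neither p nor d, nor the sign of d.

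Illustration, by assumption only, with p = 0.25:
- d = 1 mmHg: 0.25 × 1 = 0.25 mmHg
- d = 2 mmHg: 0.25 × 2 = 0.5 mmHg
- d = 4 mmHg: 0.25 × 4 = 1.0 mmHg
- d = 6 mmHg: 0.25 × 6 = 1.5 mmHg

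One way to reach p = 0.25 is half the records at a visit falling under the schedule before Amendment 4, and half of those holding two readings: 0.5 × 0.5 = 0.25. With p = 0 or d = 0 the offset is zero.

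**Step 4: the two possible repairs.**
- Last reading at both ends: last − last = 0 at visits with several readings, and single − last = 0 at visits with one. The offset is zero for any d.
- First reading at both ends: first − first = 0 at visits with several readings. For a subject with two readings on Day 1 and one at a later visit, it is single − first = −d. The offset moves to the one-reading visits.

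A simulation of 240 subjects (4,000 replicates, no true change, assumed between-subject SD 12 and within-visit SD 7 mmHg) agreed with the algebra. For d = 2 and 4, first minus last gave 2.0 and 4.0. Last minus last gave 0.0 for both. A single reading minus a first-reading baseline gave −2.0 and −4.0. This confirms the formulas only; it says nothing about what d is in this study.

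**The case against.** The case on the other side is substantial, and much of it stands.

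- **The rule is conditional.** The first reading is used only if there are several. The current protocol schedules one pre-infusion set, and with one reading first and last are the same. This stands.
- **The log does not show duplicate data.** It shows that a listed step was removed. One reading may have served both steps, and the same amendment also deleted a duplicate line for Cushingoid features. This stands; p is unknown and could be near zero.
- **The effect on conclusions is limited.** Protocol 7.3.1 rests the safety assessment mainly on adverse events. Vital signs are supporting variables, described without formal testing. This stands, and it is why the point is minor.
- **The programming plan may settle it.** That document is separate and not available here, and Day 1 is itself a dosing visit, so the first-reading rule might be meant for baseline too. This stands only as a possibility. The SAP text does not say so, and using the first reading at both ends would leave −d wherever a subject has two readings on Day 1 and one later.

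A reader might infer two stronger things. One is that the rule builds in a rise at early visits that vanishes at Amendment 4 and looks like a dose effect. The documents do not support this: neither the frequency of double readings nor the sign of d is known, the tables are not split by dose, and Protocol 4.5.3 applies the new dose from the visit after approval. Subjects would thus reach the amendment at different study visits, and one visit's table may mix both schedules. The other is that the rule inflates counts beyond the Appendix F limits. It does not, because that classification considers every measurement.

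**Conclusion.** The point holds as a minor inconsistency. Where several pre-dose readings exist, the SAP as written reports first reading at the visit minus last reading at baseline, and the Day 1 by-visit value need not equal baseline. Confidence in the rule mismatch is high.

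Confidence in its size is low. The offset is p × d; 0.25 to 1.5 mmHg follows only from the assumed p = 0.25 and d of 1 to 6 mmHg, and the true value may be zero. Any offset may shrink as Amendment 4 takes effect, but the documents do not show that there was one to shrink.

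**What to change.** In the SAP 3.8.6.1 sentence on several pre-dose readings, change first to last, so that by-visit presentations use the last measurement before dosing. This matches the SAP 3.1 baseline rule. It also selects the near-infusion reading, which the current protocol schedules and which, by the amendment log, was not the step removed. Leave the clause on the treatment-emergent classification as it is.

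Do not repair the mismatch by moving baseline to the first reading, for the reason shown in the working.

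The cost is one word in the SAP and the matching line in the programming plan. No new data are needed.

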3.8.6.2 Electrocardiogram

The investigator or qualified designee will review and indicate if the ECG is normal or abnormal. ECG results and shift from baseline will be summarized by visit.

3.8.6.3 Cushingoid features

Cushingoid features results will be summarized by visit.

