4.5.2.1 Corticosteroids

When OCS treatment is above a total dose > 40 mg/day for a dosing period > 14 days, dosing with MEDI546 may be continued, unless there is a safety concern.

However, it should be noted that frequent steroid use above Study CD-IA-MEDI-546-1013 baseline for SLE disease control (> 2 times every 6 months, higher doses [> 40 mg/day], and/or longer duration than permitted by the protocol) after 12 months of open-label MEDI-546 should result in discontinuation of MEDI-546 administration for failure to achieve a favorable benefit:risk profile.

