5.2.2 Physical Examination, ECG, Weight, Cushingoid Features, and Pap Smear

A complete physical examination will be performed at intervals designated in the schedule of study procedures and include the following examinations: head, eyes, ears, nose and throat, lungs, heart, abdomen, joints, muscles and soft tissues, neurologic system, skin, and lymph nodes; body weight will be captured according to the Schedule of Study Procedures (Table 5.1-1). Medically significant changes from Day 1 physical examination will be recorded as AEs.

A computerized 12-lead ECG will be performed according to the Schedule of Study Procedures (Table 5.1-1 and Table 5.1-2). The investigator or qualified designee will review and indicate if the ECG is normal or abnormal. Any medically significant changes from the Study CD-IA-MEDI-546-1013 Day 396 ECG will be recorded as an AE.

Subjects will be assessed for Cushingoid features at Day 1 (if appropriate) and at Q48W. Features, such as moon face, buffalo hump, purple or violaceous striae, central obesity, hirsutism, acne, easy bruising, and fragile skin, will be captured separately to evaluate whether resolution of same can occur over time with OCS reduction.

A Pap smear will be performed in females only at Week 144 (Visit 37). Subjects with an abnormal Pap smear result of high-grade squamous intraepithelial lesion (CIN-3/CIN III carcinoma in situ) or endocervical adenocarcinoma in situ will discontinue investigational product. In the event a female subject discontinues prematurely, a repeat Pap smear must be performed as part of the Early Discontinuation Visit.

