2.4 Sample Size

Sample size estimation is based on the number of subjects who have completed the treatment period of study CD1013. A total of 307 subjects have been randomized in study CD1013. Assuming that 20% of subjects will be lost to follow up or discontinue from study CD1013, there will be a total of approximately 240 subjects who will be eligible for this long-term safety study.

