3.3 Study Subjects

3.3.1 Subject Disposition and Completion Status

The number of subjects enrolled in the CD1145 study will be summarized overall and by site number. In addition, disposition of subjects throughout the CD1145 study with respect to completion of treatment will be provided overall and overtime (year 1, year 2, year 3). Disposition of subjects with respect to completion of study will also be provided.

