3.4 Exploratory Efficacy Endpoints and Analyses

3.4.4 Handling of Dropouts and Missing Data

If one or some components of SLEDAI-2K are missing, then the last observation carried forward (LOCF) approach will be used to impute the missing component score. No imputation will be performed for missing data in other variables.

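### Cushingoid features are recorded to see whether they resolve as oral steroids are reduced, but the visible SAP text plans only a by-visit summary with no shift from baseline

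*SAP*

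**What the plan says.** Protocol 5.2.2 gives the reason for the measure: the individual features "will be captured separately to evaluate whether resolution of same can occur over time with OCS reduction". On timing it states: "Subjects will be assessed for Cushingoid features at Day 1 (if appropriate) and at Q48W". In Protocol Table 5.1-1 that means Day 1 and Weeks 48, 96 and 144. The Day 1 value may be taken from Day 365 of the parent study (CD1013). The assessment is not scheduled at Week 156, at the Visit 41/Early Discontinuation Visit, or at the later follow-up visits.

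The analysis in SAP 3.8.6.3 is one sentence: "Cushingoid features results will be summarized by visit". The section immediately before it, SAP 3.8.6.2, reads "ECG results and shift from baseline will be summarized by visit". Shifts from baseline are also planned for laboratory parameters (SAP 3.8.5) and for ANA and ENA (SAP 3.7.1). SAP 3.7.1 additionally restricts a summary to subjects who were abnormal at baseline.

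On missing data, SAP 3.4.4 carries forward missing SLEDAI-2K components and then says "No imputation will be performed for missing data in other variables".

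**The concern.** Resolution with steroid reduction needs three facts about the same person: the feature was present at baseline, it was absent later, and the OCS dose had or had not come down. A by-visit summary gives only the marginal count at each visit. It does not show who lost a feature, it offsets losses against new onsets, and it carries no dose information. The visible concomitant-medication summary (SAP 3.3.4) is by ATC class and preferred term, so it does not show dose reduction either.

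The denominator also changes over three years. With no imputation and no assessment at early discontinuation, each later percentage rests on whoever is still attending. A fall might then be read as a steroid-sparing benefit when part or all of it is attrition. Loss in the opposite direction would hide real resolution.

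**Working it through.** **The plan's own figure.** SAP 2.4 states "A total of 307 subjects have been randomized in study CD1013" and assumes 20% loss: 307 × (1 − 0.20) = 245.6, consistent with the stated 240 or so. No other stated figure bears on this point.

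**Inputs not in the documents.** Baseline prevalence p, dropout among subjects with features d1, and dropout among those without d0 are not given. All values below are assumptions.

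**Formula.** Suppose nobody resolves and nobody has a new onset. Observed prevalence at a later visit is then

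p(1 − d1) / [p(1 − d1) + (1 − p)(1 − d0)].

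The fall from p, in percentage points, with zero resolution:

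| Dropout with / without features | p = 10% | p = 20% | p = 30% | p = 40% |
|---|---|---|---|---|
| 30% / 30% | 0 | 0 | 0 | 0 |
| 40% / 30% | 1.3 | 2.4 | 3.1 | 3.6 |
| 50% / 30% | 2.6 | 4.8 | 6.6 | 7.7 |
| 60% / 20% | 4.7 | 8.9 | 12.4 | 15.0 |

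**One table, two explanations.** Take N = 240 and p = 30%, so 72 subjects have the feature and 168 do not.

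- Dropout 50% with and 25% without features, nobody resolving: 72 × 0.50 = 36 and 168 × 0.75 = 126 remain. The by-visit table goes from 72/240 (30.0%) to 36/162 (22.2%), a fall of 7.8 points with no resolution.
- Dropout unrelated to features: of the same 162 remaining, 162 × 0.30 = 48.6 had the feature at baseline. Seeing 36 means net resolution of 48.6 − 36 = 12.6, and 12.6/48.6 = 26%.

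The planned summary looks the same in both cases. In the first, a shift table would show 0 resolved, 36 persisting and 36 not assessed among the 72.

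**Netting.** Twenty resolutions and twenty new onsets leave the by-visit count unchanged.

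**Baseline timing.** If the parent Day 365 value is used and this study starts after the parent Day 422 visit, the nominal gap is at least 422 − 365 = 57 days. Parent-study visit windows are not in these documents, so this is a nominal figure only.

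**The case against.** Several points on the other side have force.

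- **Hidden text.** SAP 3.4.1 to 3.4.3 and the exploratory objectives are not visible, and SAP 1 leaves table templates to a separate programming plan. A steroid analysis or a shift table could be there. This stands as a limit: the gap is shown for the section that governs this variable, not for every document.
- **Listings.** SAP 3.1 provides data listings sorted by subject number, so an individual's course over at most four assessments could be read off. A reader might infer that the question cannot be answered at all. That goes too far: the data can answer it, but the planned summary does not.
- **Complete follow-up.** If every subject were assessed at every visit, a net fall would give a lower bound on the number resolved. A three-year extension with no imputation and no assessment at discontinuation cannot rely on that.
- **The steroid rule.** Protocol 4.5.2.1 says that certain steroid use "after 12 months of open-label MEDI-546 should result in discontinuation of MEDI-546 administration for failure to achieve a favorable benefit:risk profile". A reader might infer that this makes selective loss of subjects with features likely. The documents do not support that. The rule concerns frequent use above the parent-study baseline for SLE control; it does not address persistent Cushingoid features or a stable baseline dose. It also applies only after 12 months, whereas Week 48 is day 336 (48 × 7). Selective loss before Weeks 96 and 144 is possible, but not shown to be likely.
- **A shift table does not remove dropout bias.** Assume 50% truly resolve, with 80% of resolvers and 60% of persisters retained. The observed-case rate is then 0.40/(0.40 + 0.30) = 57%. This stands, and is why the table needs a not-assessed count.
- **Confounding.** Protocol 4.5.2.3 has investigators adjust background medication to disease activity, so a comparison by OCS reduction is not causal. This also stands.

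**Conclusion.** The mismatch between purpose and analysis is real: the protocol asks about resolution with OCS reduction, and the visible SAP text for the variable gives by-visit marginals only. The SAP already uses the missing method for three neighbouring kinds of data.

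A false fall requires more dropout among subjects with features; equal dropout gives none. Over the assumed prevalences of 10% to 40% and the dropout patterns tabulated, the fall with zero resolution runs from 0 to 15 points. The true size is unknown. It would be wrong to conclude that the planned summary will mislead: it can, and it offers no way to tell whether it has.

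The consequence is confined to one descriptive safety measure. The TEAE/TESAE summaries, the immunogenicity analysis and the sample size are not affected.

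**What to change.** In SAP 3.8.6.3, add a per-feature shift from baseline at Weeks 48, 96 and 144:

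- Among subjects with the feature at baseline: numbers resolved, persisting and not assessed, with denominators. Reporting not-assessed subjects lets the reader bound the result. In the example above, 0 resolved and 36 not assessed out of 72 means between 0/72 (0%) and 36/72 (50%).
- Among subjects without it: numbers with new onset and not assessed.
- Resolution shown descriptively by whether daily prednisone-equivalent OCS dose at the visit is lower than at baseline, labelled as a post-baseline split with no causal reading. Protocol Appendix 6 already gives example dose equivalents.
- Where the baseline feature value comes from parent Day 365, use the OCS dose on that date if parent-study data can be linked. Otherwise use the Day 1 dose and note the mismatch.

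If the programming plan or the non-visible SAP text already contains such a table, a cross-reference in 3.8.6.3 is enough.

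The cost is one extra descriptive table, with no change to visits or conduct. Features are already captured separately, and Protocol 4.5.2 already records OCS dose with start and stop dates from Day 1. Recording in this study from Day 1 may not supply the parent Day 365 dose, so a link to parent-study medication data may be needed.
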